**Gingival crevicular fluid characterization during orthodontic treatment**

**[name]**

**Associate Professor**

**Department of Orthodontics, College of Dentistry,**

**University of Illinois at Chicago**

**V3; 6/22/2017-Recent IRB approval 10/3/2018-10/2/2021**

## Gingival crevicular fluid and orthodontic treatment

During Orthodontic tooth movement, teeth are moved through alveolar bone under applied forces. The applied mechanical loading force must be transferred to the alveolar bone via periodontal ligament (PDL) [1]. This process of mechanotransduction stimulates bone remodeling during which osteoblasts produce bone on the tension side and osteoclasts resorb bone on the compression side of the PDL [2-6]. Complex interactions between osteoblasts and osteoclasts involve numerous biologic molecules including cytokines and growth factors [7]. During the tooth movement, the expression of cytokines such as interleukin (IL)-1 $\beta$ , IL-6, IL-8, prostaglandin E2, RANKL and MMP1 in PDL will be up-regulated [8-10]. The sequence of events from the mechanotransduction commanding the tightly controlled accomplishment of osteogenesis at tension sides and osteoclastogenesis at compressive sides is not completely understood [11, 12].

The gingival crevicular fluid (GCF) is a transudate of interstitial tissues which is produced by an osmotic gradient [13] and it is released into the crevicular crevices at a flow rate of about 3  $\mu$ l/h [14]. Orthodontic treatment is triggered by an inflammatory process and it has been hypothesized that the quantification of specific biomarker within the GCF can be determined using Periotron [15]. However contrasting results have been reported in the literature, which studies showing both increased or unchanged GCF volumes incident to orthodontic treatment.

Given that the orthodontic treatment is triggered by a set of inflammatory cytokines which are released into the crevicular fluid during the mechanical loading, and its homeostasis is dependent on mechanical stimulation. An understanding of the biological response of crevicular fluid to mechanical loading could further advance the knowledge of orthodontic treatment.

In this study, we will investigate the biological response of gingival crevicular fluid before and after the initial wire placement of orthodontic treatment to determine the differentially expressed genes and proteins related to mechanotransduction.

## Materials and Methods

### *Eligibility criteria for the collection of gingival crevicular fluid*

One Hundred Healthy, non-smoking patients aged 11-35 years old who require orthodontic treatment with first premolar extraction at the orthodontic clinic at College of Dentistry, University of Illinois at Chicago (UIC) will be included. The informed consent will be presented to patients and parent(s) [legal guardian(s)] and signed before the procedure. The patient will be screened for the inclusion criteria at time of consent. The written assent will also be obtained from minor subjects. Before the treatment, periapical radiographs will be taken on both maxillary canines to verify the root length and morphology so the pre-fabricated power arms on the canine brackets will be closed to center of resistance of the canines. Fixed orthodontic appliances (0.018-in; MBT prescription) will be placed in the subject with an auxiliary vertical slot in the maxillary canine brackets (Dentsply International, York, NY) to accommodate the prefabricated power arms. The subjects will be referred for extraction of the maxillary first premolars. A temporary anchorage device will be placed between maxillary second premolar and maxillary first molar, 5 mm from alveolar crest for anchorage and reference purposes. The teeth in maxillary arch will be leveled and aligned before canine retraction. Once

0.016x0.016 stainless steel archwires (Dentsply International) are placed, the canine retraction will be achieved using calibrated 70-g [127] nickel-titanium closing-coil springs (Dentsply International) connected from a temporary anchorage device to the power arm on the canine brackets that allowed application of the force closer to the center of resistance of the tooth.

#### *Collection of gingival crevicular fluid*

Patients will be seated in the dental chair in an upright position. The selected site will be air-dried and isolated with cotton rolls. Without touching the marginal gingiva, supragingival plaque will be removed to avoid contamination of the paper strips. The absorbent paper strips will be placed gently in the sulcus and the absorbed paper strips will be pooled and placed in a sterile eppendorf tube containing 200 ul of phosphate buffer saline. The collected sample will be coded with unique ID numbers and kept at -80C until analyzed. The key for the IDs will be kept in a locked cabinet in Rm#237B , College of Dentistry. The patient will be informed not to take NSAIDs but paracetamol after the orthodontic treatment. The collection of GCF will be performed before bracket placement, before canine retraction, 2 weeks after canine retraction, 5 weeks after canine retraction and 7 weeks after canine retraction.

#### *Compensation for the study*

The subjects will be given the money compensation for travel expense for \$100 after the completion of the sample collection.

#### *Intraoral scanning*

The patients' occlusion and jaws will be scanned using an intraoral digital scanner. The intraoral scanning will be performed at the highest resolution at each studied timepoint. The scanning data will be exported as stereolithography binary file format (.stl) and imported to a sophisticated processing software package (Geomagic® Control 14, Geomagic®, Research Triangle Park, NC, USA). The miniscrews and palatal rugae structure will be used as reference points

#### *Wire placement and orthodontic treatment*

The patients will be bonded with brackets and 0.016x0.016" stainless steel wire will be placed and ligated onto the brackets with rubber rings. The patient will be scheduled to come back for the orthodontic treatment according to the sample collection time and once a month after the study.

#### *ELISA*

The GCF samples will first be homogenized for 30 s and centrifuged for 5 min at 1500 g to elute. The elute will then used as sample for ELISA estimation from GCF samples. The GCF sample will be detected IL1, IL6, IL8, OPG and RANKL. The ration of OPG and RANKL will be calculated and determine the potential of PDL to activate osteoclasts.

#### *microRNA analysis*

Total RNA will be extracted from the stored GCF samples using miRNeasy serum/plasma kit (Qiagen, Valencia, CA). Quantity of the total RNA will be determined by NanoDrop spectrophotometer (Thermoscientific). The total RNA will be subjected to quantitative realtime RT-PCR using Taqman® microRNA RT-PCR assays specific to hsa-miR-21, -29a, b and c. hsa-let-7d, g and i will be used as an internal control [112, 129]. The samples from each subject will be analyzed using a 7900HT realtime PCR system (Applied Biosystems).

### **Statistical Analysis**

All the analyses will be performed in triplicate for three independent experiments to confirm reproducibility of the results. Quantitative data will be presented as means  $\pm$  SD from three independent experiments. Wilcoxon Sign-ranked analysis will be used to determine the mean difference before and after treatment at  $P = 0.05$ .

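### The plan takes its means and SDs over three experiments, not over patients, so error bars produced as written would show assay variation only

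*Combined protocol and SAP*

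**What the plan says.** The Statistical Analysis section has three sentences.

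- The first sets the replication scheme and its purpose: "All the analyses will be performed in triplicate for three independent experiments to confirm reproducibility of the results".
- The second says how results are shown: quantitative data as means with "SD from three independent experiments".
- The third names the test: "Wilcoxon Sign-ranked analysis will be used to determine the mean difference before and after treatment", at the 0.05 level.

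The section does not mention patients. Elsewhere, the eligibility section enrols "One Hundred Healthy, non-smoking patients aged 11-35 years old", and the fluid collection section samples each patient "before bracket placement, before canine retraction, 2 weeks after canine retraction, 5 weeks after canine retraction and 7 weeks after canine retraction". The microRNA section says "The samples from each subject will be analyzed using a 7900HT realtime PCR system". That sentence names the instrument; it does not say how results are summarised over subjects. The ELISA section has no rule for replicates or summaries.

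**The concern.** The independent unit in this study is the patient. Replicate wells and repeat runs of the same fluid sample show how well the assay agrees with itself. They do not show how much patients differ, or how much the change differs from one patient to the next.

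The plan ties its only descriptive summary to the experiments whose stated purpose is to confirm reproducibility. A reader of a report on 100 patients will take a mean with an SD as the spread among patients. If the sentence is followed as written, that reading is wrong. No other planned output would show the spread between patients or the spread of the within-patient change. The plan also does not say how up to nine determinations per sample become the one value that a paired test needs.

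**Working it through.** The plan gives no SD, effect size, power or sample-size derivation, so there is no figure of its own to reproduce. The check has three parts.

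**1. Units in the plan.**

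| Item | Value | Source |
|---|---|---|
| Patients | 100 | Eligibility criteria |
| Visits per patient | 5 | Collection of gingival crevicular fluid |
| Patient-visit samples | 100 × 5 = 500 | arithmetic |
| Determinations per sample and marker, if every sample goes into every run | 3 × 3 = 9 | Statistical Analysis |
| Stated basis of mean and SD | 3 experiments | Statistical Analysis |
| Level of the test | 0.05, sidedness not stated | Statistical Analysis |

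**2. Can the test share the unit of the summary?** The smallest exact signed-rank p-value for n pairs arises when all differences have the same sign. It is 2/2^n two-sided and 1/2^n one-sided.

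- n = 3: 2/8 = 0.25 two-sided, 1/8 = 0.125 one-sided. The 0.05 level cannot be reached.
- n = 5: 2/32 = 0.0625 two-sided, 1/32 = 0.031 one-sided.
- n = 6: 2/64 = 0.031 two-sided.

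At least six pairs are needed two-sided, or five one-sided. Three experiments cannot supply them. A before-after contrast on fluid from 100 patients is naturally paired by patient, so the test and the stated summary use different units.

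**3. What would the reported SD contain?** Let σb² be the variance between patients, σr² the run-to-run variance for a sample, σw² the variance between wells, and m the wells per run. The documents give a value for none of these variances.

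- *SD over three runs of one sample:* variance σr² + σw²/m. There is no σb² term.
- *SD of three experiment means, with the same patients in each run:* the patient effects are common to all three means and cancel. Again there is no σb² term.
- *SD of all patient-by-run values pooled:* variance about σb² + σr² + σw²/m. This contains the patient variance and overstates it.
- *Each patient assayed in only one of three runs, all values pooled:* σb² is present.
- *One averaged value per patient, SD over patients:* variance σb² plus an assay part reduced by averaging.

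The first two are the literal readings, and both omit between-patient variance. The next two are looser readings that keep it. The direction of the error therefore depends on the reading, and its size depends on variances that the documents do not give.

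Even a correct SD at each visit does not give the spread of the change. For visits with SDs s1 and s2 and within-patient correlation ρ, the variance of the change is s1² + s2² − 2ρ·s1·s2, and ρ cannot be recovered from visit-level summaries. The SD of the change has to be reported itself.

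**The case against.** The strongest reply is that the sentence is customary laboratory wording and that the investigators mean patient data obtained in replicated assays. The 100 patients, the individually coded samples and the reference to each subject's samples support this, and the test makes sense only on patient pairs. The authors may well have meant it. But no section says so, and the same three experiments appear in the sentence that gives their purpose as reproducibility. As an instruction to an analyst, the text points to the wrong unit.

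A second reply is that inference is untouched. This stands. A reader might infer that the signed-rank test will be run on three experiments, or on replicates counted as if they were patients. The documents do not support either. The first could never reach the stated level, and nothing in the text proposes entering replicates as separate pairs.

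A third reply is that no size can be attached to the error. This also stands. A reader might infer that the SD will be too small by some known factor. That would need variance components from outside the documents, and under the pooled reading the SD would be too large.

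A fourth reply is that the documents do not show every sample going through all three runs. Each pooled sample is placed in 200 µl. Five ELISA markers at nine determinations each is 45 wells, or 200/45 = 4.4 µl of undiluted eluate per well, before any RNA extraction. Dilution could make this workable, but the documents do not say. The fix should therefore not require three runs per sample.

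**Conclusion.** The point holds for the descriptive summaries and should be fixed. Followed as written, the plan's only measure of spread is between-run assay variation, which is reproducibility in the plan's own term, and it contains no between-patient variance. The plan's paired test needs a different unit, the patient.

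The size is unknown from the documents and the direction depends on the reading, so no factor is claimed. The conclusion rests on the literal wording and on the absence of any patient-level summary rule elsewhere. It does not claim that the investigators will ignore patients, and it does not question the test, for which naming the unit of pairing is only a clarification. Confidence is moderate because the intent may differ from the wording.

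Which visits form the before-after comparison is a separate clarification. The introduction refers to sampling "before and after the initial wire placement of orthodontic treatment", while the collection schedule has two visits before canine retraction and three after. That point is not part of this finding.

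**What to change.** Keep the first sentence of the Statistical Analysis section as a reproducibility check. Replace the second with:

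*All determinations available for a sample (replicate wells, and repeat runs where done) are averaged to one value per patient, visit and marker. Means and SDs are taken over patients, with n stated, and the within-patient change is reported with its SD. The signed-rank test pairs within patient. Assay precision is reported separately.*

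The laboratory should add the scale on which replicates are averaged, in particular for the RT-PCR data.

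The cost is a change of wording. Sampling and laboratory work stay as they are, and no extra assays are required, because the rule uses whatever determinations exist. The downside is that reported error bars may be wider than under the literal wording.

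### The only rule for declaring a marker differentially expressed is an unadjusted 0.05 test applied to ten markers, with no primary marker, no named visit pair and no error control

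*Combined protocol and SAP*

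**What the plan says.** The Statistical Analysis section is the whole analysis plan. Its one inferential sentence reads "Wilcoxon Sign-ranked analysis will be used to determine the mean difference before and after treatment at" P = 0.05. The rest covers triplicate experiments and the reporting of means and SDs.

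Markers, from the ELISA and microRNA analysis sections:

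- Five proteins: "The GCF sample will be detected IL1, IL6, IL8, OPG and RANKL".
- One derived quantity: "The ration of OPG and RANKL will be calculated and determine the potential of PDL to activate osteoclasts".
- Four microRNAs: "assays specific to hsa-miR-21, -29a, b and c". The let-7 assays are internal controls and are not counted here.

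The introduction gives the aim as comparing crevicular fluid "before and after the initial wire placement of orthodontic treatment to determine the differentially expressed genes and proteins related to mechanotransduction".

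The collection section sets five sampling times: "before bracket placement, before canine retraction, 2 weeks after canine retraction, 5 weeks after canine retraction and 7 weeks after canine retraction".

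Nowhere does the document name a primary marker, a pair of collections to compare, a multiplicity adjustment, a false discovery rate or an exploratory label.

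**The concern.** The deliverable is a list of markers said to change, so the error rate that matters is that of the list. A 0.05 rule applied marker by marker controls each test and leaves the list uncontrolled. The analysis section names no subset of markers, so I read all ten as tested.

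The before/after pair is also open, so the number of tests is unknown. The introduction anchors it to initial wire placement, the analysis section to treatment, and the collection schedule to bracket placement and canine retraction. The documents also place the 0.016x0.016 stainless steel wire at two different stages. The wire placement section describes it with bonding. The eligibility section describes it after levelling and alignment ("The teeth in maxillary arch will be leveled and aligned before canine retraction"), just before retraction. These passages must be reconciled.

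With neither marker nor pair fixed in advance, any marker at any week that falls below 0.05 could be presented afterwards as the main result.

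**Working it through.** **Inputs from the document.** Level 0.05, sidedness not stated; 100 patients; 5 proteins + 4 microRNAs = 9 measured markers; 9 + 1 ratio = 10 tests per contrast; five collections.

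**Assumptions, not in the document.** Between-marker correlation 0 to 0.8; 100 complete pairs; two-sided tests; one contrast per marker, following the singular wording of the analysis section.

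**The plan's own figure.** One marker and one pair: 1 − 0.95^1 = 0.05. The stated level is right for a single test.

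**Chance of at least one false marker, independent tests.** With m null tests it is 1 − 0.95^m:

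- m = 5: 1 − 0.95^5 = 22.6%
- m = 9: 1 − 0.95^9 = 37.0%
- m = 10: 1 − 0.95^10 = 40.1%

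The ratio is built from OPG and RANKL, so ten fully independent tests are not attainable. Simulation used signed-rank tests, 100 pairs, nine equicorrelated markers and log OPG minus log RANKL as the tenth.

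| Null tests, one contrast | Correlation 0 | 0.3 | 0.5 | 0.8 |
|---|---|---|---|---|
| Five (OPG and the four microRNAs) | 23% | 20% | 19% | 13% |
| All ten | 38% | 34% | 30% | 21% |

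The five-null case follows the introduction's expectation that IL-1β, IL-6, IL-8 and "RANKL and MMP1 in PDL will be up-regulated"; a change in RANKL with OPG unchanged also moves the ratio. Carrying that expectation from the ligament to crevicular fluid is itself an assumption.

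More contrasts raise these figures. As one illustration that the plan does not state, comparing the pre-retraction sample with weeks 2, 5 and 7 gives 72% to 45% with all ten markers null.

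**False discovery rate of the present rule.** With m0 null and m1 changed markers and independent tests, FDR = Σ Bin(V; m0, 0.05) × Bin(T; m1, power) × V/(V+T), over V ≥ 1.

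| Markers truly changed, of ten | 80% power | 50% power |
|---|---|---|
| 0 | 40% | 40% |
| 2 | 15% | 20% |
| 5 | 5.0% | 8% |
| 6 | 3.5% | 5.5% |

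**Which pairs span the initial wire.** Every pair that starts before bracket placement does: the first collection against any of the other four. On the eligibility section's sequence, only the first two collections do so without canine retraction in between.

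**Cost of adjusting.** The detectable paired effect at 80% power is d = (z for 1 − α/2 + 0.842) / √(100 × 0.955), where 0.955 is the efficiency of the signed-rank test for normal data:

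- α = 0.05: (1.960 + 0.842)/9.77 = 0.29 SD
- α = 0.05/9 (first Holm step, nine secondary tests): (2.773 + 0.842)/9.77 = 0.37 SD
- α = 0.05/10 (strictest Benjamini-Hochberg step, ten tests): (2.807 + 0.842)/9.77 = 0.37 SD

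**A remedy that does not work.** Suppose a primary is tested alone at 0.05 beside a Benjamini-Hochberg family of the other nine. With all null and independent, the false discovery rate of the full list is 1 − 0.95 × 0.95 = 9.8%. By simulation it falls to about 6% at correlation 0.8.

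**The case against.** The strongest reply is that this is a single-arm characterisation study with no treatment comparison, so strict family-wise control is partly a matter of preference. If the markers expected in the introduction do change, five of ten tests are non-null, and the false discovery rate of the present rule is already about 5% at 80% power. That is fair, and it is why a discovery option belongs in the fix. But the result depends on how many markers change and on power, neither of which the plan controls or states. It is 15% with two changed markers at 80% power, and 8% with five changed at 50% power. The plan also never calls its results exploratory.

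Triplicate experiments do not answer the point. Their stated purpose is reproducibility, and they give no control across markers or visits.

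A reader might infer more than the documents support:

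- *That only the first two collections can bracket the initial wire.* Any pair starting before bracket placement does, and the two descriptions of the wire leave open which wire is the initial one.
- *That the false share is near 5% only if half the markers change with at least 80% power.* It is 5.5% with six of ten changed at 50% power.
- *That a false marker is more likely than not.* The 72% figure needs every marker null and several contrasts, while the analysis section's wording is singular.
- *That the individual tests are invalid.* Each keeps its 5% level.

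**Conclusion.** The point holds. The list of differentially expressed markers has no error control, and the comparison behind it is not identified. With one contrast, the chance of at least one false marker is about 13% to 23% in the milder scenario and 21% to 38% if nothing changes, against a nominal 5%. These ranges rest on assumed correlations, on all ten quantities being tested, and on which markers truly change. The absence of a primary marker, visit pair, adjustment and exploratory label is read directly from the document. This should be corrected before analysis; it does not invalidate the design or the data collected.

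**What to change.** In the Statistical Analysis section:

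1. Name the before and after collections. Reconcile them with the aim in the introduction, the treatment sequence in the eligibility section, the collection schedule and the wire placement section. List every marker-by-visit test.
2. Choose one option.
   - **Confirmatory:** one primary marker and one pair at two-sided 0.05, then Holm at 0.05 over all other listed tests, only if the primary is significant.
   - **Discovery:** Benjamini-Hochberg at a 5% false discovery rate over all listed tests in one family, with no separate unadjusted primary, labelled exploratory.
3. Call a marker differentially expressed only under the chosen procedure.

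This takes wording and a few lines of code, with no new samples. The price is fewer declared markers: with one contrast and 100 complete pairs, the detectable effect at the strictest step rises from 0.29 to about 0.37 SD. Under the confirmatory option no secondary marker can be declared if the primary fails, which has a 20% chance if the primary has 80% power.

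### The signed-rank test is said to determine a mean difference, but it addresses the pseudo-median within-patient change, and no effect estimate or interval matching it is named

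*Combined protocol and SAP*

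**What the plan says.** The statistical plan is the three-sentence Statistical Analysis section of the combined protocol and SAP.

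- The first sentence sets the replication: "All the analyses will be performed in triplicate for three independent experiments to confirm reproducibility of the results".
- The second gives the only descriptive summary, a mean with "SD from three independent experiments".
- The third gives the only inferential method and its target: "Wilcoxon Sign-ranked analysis will be used to determine the mean difference before and after treatment", at a 0.05 level whose sidedness is not stated.

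The section on eligibility sets the number of patients: "One Hundred Healthy, non-smoking patients aged 11-35 years old". The ELISA section lists the protein outcomes: "The GCF sample will be detected IL1, IL6, IL8, OPG and RANKL". It adds the ratio of OPG to RANKL.

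No section names an estimate of within-patient change, a confidence interval, or an assumption that the changes are symmetric.

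**The concern.** The quantity tested and the quantity named are not the same. The signed-rank test ranks the within-patient changes, and the effect measure that belongs to it is their pseudo-median: the median of the averages of all pairs of changes. A mean difference is a different parameter. Concentrations and ratios of concentrations are often right-skewed (an assumption here, since the document gives no distribution), and then the two can differ.

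The planned summary does not close the gap. A mean and SD over three experiments, introduced by a sentence about reproducibility, tells the reader how well the assay repeats. It does not say how much patients changed or how much they varied.

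Followed literally, the plan yields a p-value labelled as a result about the mean, with no effect size or uncertainty for what was tested, beside an SD that may reflect assay noise. The missing estimate matters even if the changes are symmetric.

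**Working it through.** The document gives no effect size, SD or power figure, so there is no stated result to reproduce. The check has two parts.

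**1. What the test targets**

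Let d₁,…,dₙ be the within-patient changes, with n = 100 (eligibility section, all patients assumed paired).

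- The signed-rank statistic equals the number of pairwise averages (dᵢ + dⱼ)/2, i ≤ j, that are positive. There are n(n+1)/2 = 100 × 101/2 = 5,050 of them.
- The test compares that count with half of 5,050, which is 2,525. The matching estimate is therefore the median of the 5,050 averages, the Hodges-Lehmann estimate.
- The null SD of the count is √[n(n+1)(2n+1)/24] = √(100 × 101 × 201/24) ≈ 290.8. Since 1.96 × 290.8 ≈ 570 and 2,525 − 570 = 1,955, the 95% interval runs from about the 1,955th smallest to the 1,955th largest average.
- The mean change does not enter. Symmetry of the changes guarantees that mean and pseudo-median coincide. It is sufficient, not necessary.

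**2. How far apart the two can be**

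From the document: n = 100 and level 0.05. Assumed: two-sided test, bivariate log-normal before and after values, log-SD 0.5, 0.8 or 1.0, log correlation 0.5 (range 0.3 to 0.7), and 20,000 simulated trials per setting. The figures concern the ELISA concentrations. The microRNA section gives no analysis scale, so they do not cover it.

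*No change.* The signed-rank test rejects in about 5% of trials (4.7% to 5.2%) at every setting. It is valid.

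*A 1.3-fold rise.* With the baseline mean set to 1, the mean change is 1.3 − 1 = 0.30, or 30% of the baseline mean. At correlation 0.5:

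| Log-SD | Mean change | Pseudo-median change | Signed-rank significant, paired t not |
|---|---|---|---|
| 0.5 | 30% | 27% | about 0.2% |
| 0.8 | 30% | 22% | about 13% |
| 1.0 | 30% | 18% | about 21% |

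Over correlations 0.3 to 0.7, the last column ranges over 0-1%, 8-13% and 17-22%. The reverse (t-test significant, signed-rank not) reaches at most about 5%. A significant signed-rank result with a sample mean of opposite sign occurs in at most 0.3%. A typical 95% Hodges-Lehmann interval at correlation 0.5 is 16-38%, 7-38% or about 3-36% of the baseline mean, which is the information that the plan would leave unreported.

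*Equal means, unequal spread.* If the log-SD rises from 0.5 to 0.6, 0.7 or 0.8 while the arithmetic means stay equal, the test rejects in about 8%, 19% or 34-35% of trials at correlation 0.5. This is correct for the pseudo-median, which is −3%, −6% or −10% of the baseline mean. It is wrong if reported as a mean difference, which is zero. A paired t-test stays at 5-6%.

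**The case against.** **The planned computation is not wrong.** The aim in the introduction is to find which genes and proteins change with loading, and a valid test of no change answers that. On this view the fault is one loose word and an unnamed estimate. The first half stands: the test need not be replaced. But this sentence is the plan's only statement of what will be estimated, so its wording decides how results are reported.

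**The sizes rest on an assumed model.** This stands. No section gives a distribution, SD or correlation, and at log-SD 0.5 the practical effect is small. The equal-means case is constructed and runs against the introduction's expectation of up-regulation. It shows that the two quantities can part, not that they are likely to here.

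**The mean and SD may be laboratory boilerplate meant to cover patients.** That is possible. Even so, a mean and SD of values is neither an estimate of within-patient change nor the quantity tested, and it carries no interval.

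**Stronger readings that do not hold.**

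- A reader might infer that the signed-rank test is invalid here. It holds its level under no change.
- A reader might infer that results could point the wrong way. Under a proportional rise this almost never happens.
- A reader might infer that the test will be run on three experiments, where the smallest two-sided p-value is 2/2³ = 0.25. The text attaches the three experiments to the summary and to reproducibility. It does not say that they are the units of the test.

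**Conclusion.** The point holds as a mismatch between the test and its stated target, together with a missing estimate. The test can stay. The label is wrong as written, and the only planned summary, read literally, does not describe change across patients.

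The size is conditional on the log-normal model: the mismatch is negligible to modest when skewness is mild and material at log-SD 0.8 to 1.0. The need for an estimate with an interval does not depend on that model. This is a change that should be made; it does not threaten the validity of the study.

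**What to change.** Amend the Statistical Analysis section along these lines:

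*Replicate assay values are averaged within patient and visit. The pseudo-median within-patient change between the named collections is tested with the Wilcoxon signed-rank test at the 0.05 level, with the patient as the unit. It is reported as the Hodges-Lehmann estimate with a 95% confidence interval beside the p-value. The SD of assay replicates is reported separately from the spread across patients.*

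The cost is a few sentences and standard software, with no new data and no change of test. Analysis on the log scale, or a paired t-test if the arithmetic mean is truly wanted, is an option and not part of the required change. The collection section lists five time points ("before bracket placement, before canine retraction, 2 weeks after canine retraction, 5 weeks after canine retraction and 7 weeks after canine retraction"), so the plan must also name the pair to be compared. That is a separate point.
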